### **3.3 *Exclusion criteria***

A patient who meets any of the following criteria will be excluded from the study:

1. Patients receiving any other agent (investigational or not) with potential anti-neoplastic activity within 3 weeks prior to obtaining the baseline tumor specimen for biomarker evaluation.
2. Patients receiving concomitant radiation
3. Prior treatment with an agent targeted at the insulin-like growth factor-1 receptor
4. History of allergic reactions attributed to compounds of chemical and biological composition similar to those of cetuximab or IMC-A12
5. Pregnant patients, or patients who are breast feeding (patients who have a positive pregnancy test within the first 30 days before the first dose of treatment are excluded)
6. Patients with uncontrolled illnesses which, in the opinion of the investigator, could be aggravated by the administration of the study drug(s)

### **3.4 *Patient enrollment***

All patients meeting the eligibility requirements will be considered for enrollment regardless of sex, race, or religion. Discussions regarding protocol enrollment and patient eligibility will begin with any of the investigators named on the protocol. Patients will be made aware of the protocol, its specific aims and objectives, and the potential risks and benefits the patient may incur. Each patient or patient's legally acceptable representative will be required to read, agree to, and sign a current Institutional Review Board (IRB)-approved informed consent form prior to being enrolled and/or any study-related procedure is performed. There will be no financial compensation for patients enrolling on this protocol. Baseline evaluations will be performed as described in section 7.1.

### **3.4.1 Screening**

Patients will be referred from the head and neck surgical or medical oncology clinics for consideration for participation in this study. The trial has the full support of the chairs of the departments of Thoracic/Head and Neck Medical Oncology and Head and Neck Surgery. As part of this collaboration, we have added this clinical protocol to an interactive database managed by the department of Head and Neck Surgery. This database will alert research personnel of patients with certain characteristics, such as potentially resectable head and neck cancer, that have been evaluated for the first time in the Head and Neck Surgery clinic. Through this mechanism, these patients may be identified and, after obtaining permission from the primary attending physician, the patients will be contacted to discuss possible participation in this clinical trial. Also, eligible patients will be identified during the weekly Head and Neck planning conference, during which cases are discussed with the multidisciplinary team to define the treatment plan. These patients will also be contacted for possible study participation after obtaining permission from the primary attending physician.

## **3.5 *Methods for assigning patients to treatment groups***

Patients will be stratified according to the primary site of the head and neck cancer (i.e., non-skin primary or skin primary), and the current use of any anti-hyperglycemic pharmacologic agent and will be then randomly assigned 1:1:1 to one of the three treatment groups:

Arm A: cetuximab alone

Arm B: IMC-A12 alone

Arm C: cetuximab + IMC-A12

Patients will be assigned to each treatment arm by M. D. Anderson's computer-based CORE system. The randomization code will be generated by the study biostatistician and stored in the CORE database prior to initiation of the trial. The investigators will be

blinded to the code. Since we have two stratification factors, four sets of codes (one for each strata) will be produced. Random permuted block design with a block size of 3 or 6 will be used within each one of the four strata.

Since there is limited data on the use of IMC-A12 in diabetic patients, as added precautions, if toxicity data on this study and on the randomized phase II conducted at M. D. Anderson in the setting of platin-refractory recurrent HNSCC raise concern about including diabetic patients, additional considerations will be made to include diabetes as an exclusion criteria and, as a result, stratification of patients according to the use of anti-hyperglycemic pharmacologic agent will no longer be performed.

After enrollment, patients will be assigned a unique study identification number and cohort. The study identification number and the patient's initials will be recorded on PDMS and/or CORE databases and correspondence regarding the patient.

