## Synopsis

**Title of Study:** An exploratory study to assess the modulation of biomarkers in patients with squamous cell carcinomas of the head and neck randomized to receive preoperative treatment with cetuximab and/or IMC-A12, an anti-insulin-like growth factor-1 receptor monoclonal antibody

**Study Center(s):** The University of Texas M. D. Anderson Cancer Center, Houston, TX.

**Concept and Rationale:** Cetuximab, a monoclonal antibody directed to the epidermal growth factor receptor (EGFR), has been recently approved for the treatment of locally advanced (concurrent with radiation) or recurrent (as single agent) cisplatin-refractory squamous cell carcinoma of the head and neck (HNSCC). However, in the setting of recurrent disease, response rates to this agent are in the range of 13%. The reason why the majority of patients do not respond to EGFR-targeted drugs is poorly understood. The majority of HNSCC present overexpression and overstimulation of the insulin-like growth factor-1 receptor (IGF-1R) in cancer cells as compared to the adjacent normal mucosa. The IGF-1R shares common intracellular signaling pathways with EGFR (e.g., phosphatidyl-inositol 3-kinase/Akt/mammalian target of rapamycin [mTOR]) and might function as an EGFR-independent activator of these pathways, driving cell proliferation and survival. IGF-1R signaling has been shown to mediate resistance to EGFR or HER-2 targeted drugs in breast, colon, prostate, and non-small cell lung cancer cell lines. In HNSCC, IGF-1R blockade leads to an increase in apoptosis *in vitro*, and the combination of IGF-1R and EGFR tyrosine kinase inhibitors results in an enhanced anti-neoplastic effect as compared to either drug alone. This effect has been shown to occur through down-regulation of phospho-Akt, ultimately leading to enhanced apoptosis, in part through inhibition of m-TOR mediated survivin synthesis. Taken together, these results indicate that signaling through the IGF-1R is an important stimulus for cancer growth and might be responsible for the *de novo* and / or acquired resistance of HNSCC to EGFR-targeted drugs. Therefore, therapeutic strategies directed to the inhibition of both IGF-1R and EGFR could potentially exhibit additive or synergistic anti-neoplastic effects.

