## **4 Investigational plan**

### ***4.1 Overall study design and plan***

This randomized, open-label study will enroll approximately 60 patients (20 in Arm A, 20 in Arm B, 20 in Arm C) with HNSCC for whom surgical resection of the tumor is planned as part of the standard treatment.

After obtaining informed consent, patients will undergo baseline screening to determine eligibility. These will include clinical laboratory tests (as described in section 6.5), imaging scans (as described in section 6.7), and assessment of the baseline biopsy for confirmation of diagnosis and adequacy for biomarker evaluation. If necessary, a baseline tissue specimen will be obtained (as described in section 6.6). The tentative date of tumor surgical resection (herein defined as day 0) will be recorded. Patients will be randomized to one of the treatment arms and will receive the study drug(s), before surgery, on day -9 (+/- 3 days) and day -2 (+/- 3 days). A third dose of the study treatment(s) may be administered 7 days (+/- 3 days) after the second dose, in case surgery is delayed. Repeated imaging studies will be performed after the last treatment and before surgery.

Surgery will be performed on day 0. However, surgery may be moved up or postponed if judged necessary by the attending physician. In this event, the reason for modifying the surgical date should be recorded. Optional biopsies of skeletal muscle and adipose tissue will be obtained at the time of surgery (as described in section 6.10). A post-operative follow-up visit or telephone call is planned for assessment of toxicity (Fig. 1), in addition to the regular follow-up visits in the surgery clinic. The complete study events table is outlined in section 7.5.

[figure not shown]

Figure 1: Time-line of events during the study. C = cetuximab; A = IMC-A12.

\* A third dose of the study treatment(s) may be administered 7 days (+/- 3 days) after the second dose, in case surgery is delayed.

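### Section 3.5 prints the block sizes in the protocol of an open-label, single-centre trial, so anyone tracking a stratum can guess the next arm about 56–61% of the time (33% by chance)

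*Combined protocol and SAP*

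**What the plan says.** Section 3.5 describes a central, concealed procedure. Patients are "randomly assigned 1:1:1 to one of the three treatment groups". On the strata: "Since we have two stratification factors, four sets of codes (one for each strata) will be produced". The factors are skin or non-skin primary and current anti-hyperglycaemic medication. On custody: "The randomization code will be generated by the study biostatistician and stored in the CORE database prior to initiation of the trial". The section adds that investigators do not see the code. It then gives the sizes: "Random permuted block design with a block size of 3 or 6 will be used within each one of the four strata". It does not say whether one size is fixed or whether sizes vary at random, and it does not restrict who may know them.

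Section 4.1 removes treatment masking: "This randomized, open-label study will enroll approximately 60 patients". The Synopsis lists a single centre, "The University of Texas M. D. Anderson Cancer Center, Houston, TX".

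Other safeguards appear elsewhere. Eligibility is reviewed before randomization (section 7.1), and readers of the pharmacodynamic markers are blinded to treatment and clinical data (section 6.10.1). Before a candidate is approached, the attending physician must give permission (section 3.4.1). Expected accrual is 4 patients a month (section 3.1).

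**The concern.** Concealing a list protects allocation only if the next entry cannot be worked out from earlier ones. Here three things combine: treatment is open, one team sees every assignment, and the protocol that the team works from gives the block sizes. Both stratification factors are known before randomization, so the team also knows which list applies to the next patient.

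A person who can anticipate the next arm can influence who is put forward and when. Section 3.5 itself notes how little is known about IMC-A12 in diabetic patients, which gives a reason to prefer some assignments for some patients. Safety and glucose metabolism are secondary objectives (section 2.2), and section 12.3 allows arms B and C to be pooled against arm A for the metabolic parameters. That is the contrast that such selection would distort. With 20 patients per arm, a few selected patients can change the case mix.

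**Working it through.** **Inputs.** Three arms, 1:1:1, blocks of 3 or 6, four strata (section 3.5); open-label, 60 patients (section 4.1); one centre (Synopsis). The plan gives no figure for predictability, so there is none to reproduce. The guesser is assumed to know all past assignments in the stratum and the printed sizes, and to name the arm with the highest probability of coming next. Chance is 1/3.

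**Fixed block of 3.** The probability of a correct guess at positions 1, 2 and 3 is 1/3, 1/2 and 1.
- Correct: (1/3 + 1/2 + 1)/3 = 11/18 = 61.1%.
- Certain: the last position only, 1/3 = 33.3% (20 of 60).

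**Fixed block of 6.** Averaged over all orderings, the probability of a correct guess at positions 1 to 6 is 1/3, 2/5, 1/2, 8/15, 3/5 and 1.
- Correct: (10 + 12 + 15 + 16 + 18 + 30)/30 = 101/30, and divided by 6 this is 56.1%.
- Certain: position 6 always, and position 5 when both remaining slots are the same arm (probability 1/5). (1 + 1/5)/6 = 20.0% (12 of 60).

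**Sizes 3 and 6 mixed at random and hidden, assumed 50:50.** The guesser weighs both sizes. For example, suppose the first two patients in a stratum get A and then B.
- P(A, B | size 3) = 1/3 × 1/2 = 1/6.
- P(A, B | size 6) = 1/3 × 2/5 = 2/15.
- The posterior probability of size 3 is (5/30)/(5/30 + 4/30) = 5/9.
- P(C next) = 5/9 × 1 + 4/9 × 2/4 = 7/9 = 0.78.

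So the third assignment can be called with fair confidence, but it is not certain. Simulating this updating over a sequence of 60 gives about 57.6% correct, 8–9% certain (about 5 of 60), and 33% callable at 0.75 or more (about 20 of 60).

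**Four strata.** The documents give no stratum sizes. I assumed 42/10/6/2, 36/12/9/3, 30/15/10/5 and 15/15/15/15. Incomplete last blocks lower the figures slightly:

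| Block size | Certain | Correct guess |
|---|---|---|
| 3, fixed | 32–33% | 60–61% |
| 6, fixed | 16–18% | 53–55% |
| 3/6 mixed, hidden | 7–8% | 56–57% |

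In the mixed case 31–33% of assignments remain callable at 0.75 or more.

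**Does the next arm contain IMC-A12?** This is known for certain when no arm A slot remains, or when only arm A slots remain.
- Fixed block of 3: position 2 if the first patient got A (1/3), and position 3 always. (1/3 + 1)/3 = 44%.
- Fixed block of 6: positions 3 to 6 contribute 1/15, 3/15, 7/15 and 15/15. (26/15)/6 = 29%.

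**Larger blocks.** A hidden 50:50 mix of 6 and 9, with both sizes known as possibilities, gives about 54% correct, 5% certain and 18% callable at 0.75 or more. The price is balance. Under the first three assumed splits, the chance that the largest and smallest arms differ by 4 or more rises from about 5–6% (3/6 mix) to 15–18% (6/9 mix). The chance that an arm has fewer than 18 randomized patients rises from about 0.5% to 3–4%. Section 12.4 needs 18 evaluable patients per arm.

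**The case against.** The strongest reply has four parts.

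1. **Stratification.** Drug-treated diabetics have their own code lists, so their numbers per arm stay close to equal whoever is enrolled. This stands. A reader might infer that investigators could move diabetics as a group away from IMC-A12. Section 3.5 does not support that. What remains is the choice of which patients enter within a stratum: diet-controlled or borderline-glycaemia patients, within the entry limit of fasting glucose below 130 mg/dL (section 3.2), and frail patients.

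2. **The wording may already mean varying sizes.** This is a fair reading, and it cuts certainty from 20–33% to about 8–9%. It does not remove the problem, because correct guesses stay near 57%.

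3. **Other safeguards.** Pre-randomization eligibility review limits exclusion after assignment. Blinded marker reading limits measurement bias. Dosing is tied to a planned surgery date, which limits waiting for a preferred slot, although section 4.1 lets that date move. Section 12.2.4 reports toxicity descriptively by arm. All of this limits the consequences, but none of it governs who is put forward next.

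4. **Small blocks are defensible.** With four strata and 60 patients they protect balance, as the figures above show. This stands as an argument about which sizes to use. It is no argument for printing them.

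**Conclusion.** The concern holds as a weakness in allocation concealment. An investigator who tracks a stratum can guess the next arm about 56–61% of the time over complete blocks, or 53–61% under the assumed stratum splits, against 33% by chance. How much is certain depends on a point that the plan leaves open: 33% or 20% with a fixed, known size of 3 or 6, and about 8–9% with a hidden 50:50 mix, where about one third is still callable at 0.75 or more. The 50:50 mix, the stratum sizes and a guesser who keeps track are assumptions.

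Three stronger readings are tempting, and the documents support none of them.
- *A third of all assignments is known in advance.* That needs size 3 to be fixed and known, which section 3.5 does not say.
- *Selection has occurred, or the phospho-Akt result is biased.* The documents show opportunity only. The primary endpoint is a within-patient change read blind, so any effect would be indirect, through patient mix, and its size cannot be computed from the plan.
- *Size 3 must be dropped.* The balance figures make that a trade-off, not an error.

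The sample size does not depend on this point.

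**What to change.** In section 3.5, delete the sizes and write: *permuted blocks of randomly varying size, known only to the study biostatistician and the CORE system*. Keep the sizes in a randomization document withheld from investigators. Leave their choice, including whether to keep size 3, to the biostatistician, who should weigh predictability against imbalance with four strata and 60 patients.

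The cost is one sentence and one restricted document. If the stored code uses a single size, a new list is needed for the sentence to be true. If recruitment has begun, deletion does not undo what investigators have already read. The biostatistician should then decide whether to redraw the unused part of the code. Withholding the sizes does not in itself change balance; only moving to larger blocks does.

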## **4 Investigational plan**

### ***4.1 Overall study design and plan***

This randomized, open-label study will enroll approximately 60 patients (20 in Arm A, 20 in Arm B, 20 in Arm C) with HNSCC for whom surgical resection of the tumor is planned as part of the standard treatment.

After obtaining informed consent, patients will undergo baseline screening to determine eligibility. These will include clinical laboratory tests (as described in section 6.5), imaging scans (as described in section 6.7), and assessment of the baseline biopsy for confirmation of diagnosis and adequacy for biomarker evaluation. If necessary, a baseline tissue specimen will be obtained (as described in section 6.6). The tentative date of tumor surgical resection (herein defined as day 0) will be recorded. Patients will be randomized to one of the treatment arms and will receive the study drug(s), before surgery, on day -9 (+/- 3 days) and day -2 (+/- 3 days). A third dose of the study treatment(s) may be administered 7 days (+/- 3 days) after the second dose, in case surgery is delayed. Repeated imaging studies will be performed after the last treatment and before surgery.

Surgery will be performed on day 0. However, surgery may be moved up or postponed if judged necessary by the attending physician. In this event, the reason for modifying the surgical date should be recorded. Optional biopsies of skeletal muscle and adipose tissue will be obtained at the time of surgery (as described in section 6.10). A post-operative follow-up visit or telephone call is planned for assessment of toxicity (Fig. 1), in addition to the regular follow-up visits in the surgery clinic. The complete study events table is outlined in section 7.5.

[figure not shown]

Figure 1: Time-line of events during the study. C = cetuximab; A = IMC-A12.

\* A third dose of the study treatment(s) may be administered 7 days (+/- 3 days) after the second dose, in case surgery is delayed.

## 5 Study treatments

### 5.1 *Treatments safe handling and administration*

#### 5.1.1 IMC-A12

Patients will receive IMC-A12 6 mg/kg i.v. via infusion over 1 hour in arms B and C. In arm C, IMC-A12 will be given 1 hour after the end of the cetuximab infusion. Patients do not need to be premedicated prior to administration of IMC-A12. The dose of IMC-A12 will be dependent upon the patient's baseline body weight in kilograms. This dose will be recalculated if there is a 10% change in body weight from baseline. The dose of IMC-A12 will be aseptically withdrawn from the vial and transferred to a sterile ethylene vinyl acetate i.v. bag or an evacuated USP Type II glass i.v. container. For dose volumes < 250 mL, a sufficient quantity of sterile normal saline (0.9% weight/volume) solution will be added to the container to make the total volume 250 mL.

The container will be gently inverted to ensure adequate mixing. Different drug product lots should not be mixed in a single infusion. An infusion set with an in-line, 0.22- $\mu$ m, protein-sparing filter will be required for administration of IMC-A12. Use 0.9% normal saline to flush the line at the end of the infusion. Please see Section 5.4.1 for storage requirements for IMC-A12.

Cixutumumab is an anti-IGF-IR recombinant human monoclonal antibody of the IgG1 class. Cixutumumab drug product (DP) is a sterile, preservative-free solution for infusion of cixutumumab formulated in an aqueous solution at a concentration of 5 mg/mL (250 mg/50 mL) or 10 mg/mL (500 mg/50 mL vial) or 15 mg/mL (750 mg/50 mL). The buffer contains 10mM sodium citrate, 100mM sodium chloride, 100mM glycine, and 0.01% polysorbate 80.

Cixutumumab DP is a clear or slightly opalescent and colorless or pale yellow liquid without visible particles. The pH is 6.5. The osmolality is 310 mmol/kg.

All excipients used for the manufacture of cixutumumab DP are of pharmacopoeial grade. No animal-derived components are used in the manufacture of cixutumumab DP excipients.

#### Administration:

##### a) To administer using pre-filled IV infusion containers:

Calculate the respective dose and remove the corresponding volume of 0.9% normal saline from the prefilled 250 mL container of the correct composition. Aseptically transfer the calculated dose of cixutumumab DP to the container to bring the final volume in the container back to 250 mL. Gently invert the container to mix.

##### b) To administer using empty IV infusion containers:

Aseptically transfer the calculated dose of cixutumumab DP into an empty I.V. container of the correct composition and add a sufficient quantity of sterile normal saline (0.9% weight/volume) to the container to bring the total volume to 250 mL. Gently invert the container to mix.

Only 0.9% normal saline should be used for dilution and post-infusion flushing of infusion line.

The infusion rate must never exceed 25 mg/minute. Different lot numbers of cixutumumab must not be mixed in a single infusion.

The infusion set must be flushed post-infusion with sterile normal saline equal to or exceeding the infusion line hold-up volume to ensure delivery of the calculated dose.

**CAUTION:** Infusion reactions may occur during or following IMC-A12 administration (see Section 9.2.1 for definitions of grade 3 or 4 infusion reactions).

### 5.1.2 Cetuximab

Cetuximab is prepared by ImClone Systems under appropriate manufacturing conditions as an injectable solution, in single-use 50-mL vials containing 2 mg/mL of product.

Cetuximab requires no dilution. Different cetuximab lot numbers must not be mixed in a single infusion. Cetuximab will be administered as indicated on the package insert.

All patients will be premedicated with diphenhydramine hydrochloride, 50 mg oral or i.v. (or a similar agent), prior to the first dose of cetuximab in an effort to prevent an infusion reaction. Premedication is recommended prior to subsequent doses; however, the dose of diphenhydramine hydrochloride (or a similar agent) may be reduced or eliminated at the investigator's discretion.

Patients will receive cetuximab intravenous infusions via infusion pump or gravity drip, through a non-PVC tubing. In arms A and C, the initial dose of cetuximab is  $400 \text{ mg/m}^2$  and is administered over 120 minutes. The second and third (if applicable) dose of cetuximab is  $250 \text{ mg/m}^2$  administered over 60 minutes, in arms A and C. The dose of cetuximab is dependent upon the patient's baseline body weight in kilograms. This dose will be recalculated if there is a 10% change in body weight from baseline. The infusion rate must never exceed 10 mg/minute (5 mL/minute). Patients should be observed closely during each infusion of cetuximab. Infusion times may be increased for patients who experience grade 1 through 3 allergic reactions.

Prior to infusion, the appropriate volume of cetuximab will be drawn from the vial with a sterile syringe. Cetuximab will be transferred from the syringe into a sterile evacuated container. Cetuximab will then be filtered through a 0.22- $\mu$ m protein-sparing or low-protein binding in-line filter. At the end of the infusion, 0.9% normal saline will be used to flush the line.

**CAUTION:** Infusion reactions, including severe reactions, may occur during or following cetuximab administration. Most infusion reactions occur with the first infusion of cetuximab, but some patients' first infusion reactions have been reported following subsequent doses. The infusion reaction may occur during the infusion or may be delayed until any time after the infusion. A nurse must be present in the immediate treatment area throughout the infusion period. A physician must be in close proximity to the patient treatment area. In the event of an infusion reaction, the patient should be treated as described in Section 9.1.1. Patients should be instructed to report any delayed reactions to the investigator immediately.

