#### **9.1.1 *Cetuximab infusion reactions***

Infusion reactions may occur during a cetuximab infusion or may be delayed until any time after the infusion. Infusion reactions will be defined according to the NCI-CTCAE, Version 3.0, definition of allergic reaction/hypersensitivity, as follows:

- NCI-CTCAE Grade 1: transient flushing or rash, drug fever  $<38^{\circ}\text{C}$ 
  - ✓ Treatment: decrease the cetuximab infusion rate by 50% and monitor closely for any worsening.
- NCI-CTCAE Grade 2: rash, flushing, urticaria, dyspnea, drug fever  $\geq 38^{\circ}\text{C}$ 
  - ✓ Treatment: stop the cetuximab infusion, administer appropriate therapy, and then restart the cetuximab infusion with a decrease in the infusion rate of 50% and monitor closely for any worsening.
- NCI-CTCAE Grade 1 or 2 Infusion Reaction manifesting only as a delayed drug fever (starting after the end of cetuximab infusion)
  - ✓ Treatment: maintain the cetuximab dose and infusion rate and consider administering acetaminophen or cyclooxygenase-2 inhibitors (at the dose and schedule of the investigator's discretion) prior to the subsequent cetuximab infusion, if not otherwise contraindicated in the patient.
- NCI-CTCAE Grade 3 or 4 Infusion Reaction
  - ✓ A grade 3 reaction consists of: symptomatic bronchospasm with or without urticaria, requiring parenteral medication(s); allergy-related edema/angioedema; hypotension.
  - ✓ A grade 4 reaction (anaphylaxis) is a life-threatening event characterized by rapid onset (often within minutes) of airway obstruction (bronchospasm, stridor, hoarseness), urticaria, and/or hypotension.

Treatment of a Grade 3 or 4 Infusion Reaction:

- Stop the cetuximab infusion immediately and disconnect infusion tubing from the patient.
- Administer epinephrine, bronchodilators, antihistamines, glucocorticoids, intravenous fluids, vasopressor agents, oxygen, etc, as medically indicated.

Following a grade 3 or 4 infusion reaction, the patient is to receive no further cetuximab or IMC-A12 treatment. In the event of a grade 1 or 2 infusion reaction, the cetuximab infusion rate should be permanently reduced by 50%.

If there is any question as to whether an observed reaction is an infusion reaction of grades 1 to 4, the Eli Lilly & Co. Medical Monitor should be contacted immediately to discuss and grade the reaction.

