### **9.2.1 IMC-A12 infusion reactions**

IMC-A12 infusion reactions will be defined according to the NCI-CTCAE Version 3.0 definition of allergic reaction/hypersensitivity, as detailed below. Consistent with usual medical practice, selected parenteral medications may be utilized for grade 2 allergic/hypersensitivity reaction as detailed below. The Eli Lilly & Co. Medical Monitor should be contacted immediately if questions arise concerning the grade of the reaction.

- Grade 1: transient flushing or rash, drug fever <38°C
  - ✓ Treatment: Slow infusion rate by 50% and monitor patient for worsening of condition.
- Grade 2: rash, flushing, urticaria, dyspnea, drug fever ≥38°C
  - ✓ Treatment: Stop the infusion, administer diphenhydramine hydrochloride 50 mg i.v., acetaminophen 650 mg orally for fever, and oxygen. Resume infusion at 50% of the prior rate once the infusion reaction has resolved or decreased to grade 1; infusion duration should not exceed 2 hours. Monitor patient for worsening condition, and premedicate with diphenhydramine hydrochloride 50 mg i.v. for subsequent infusions.

- ✓ For a second grade 1 or 2 infusion reaction, administer dexamethasone 10 mg i.v.; for subsequent infusions, premedicate with diphenhydramine hydrochloride 50 mg i.v., acetaminophen 650 mg orally, and dexamethasone 10 mg i.v. (or equivalent).
- Grade 3: symptomatic bronchospasm, requiring parenteral medication(s), with or without urticaria; allergy-related edema/angioedema, hypotension

✓ Treatment: Stop the infusion and disconnect infusion tubing from the patient. Administer diphenhydramine hydrochloride 50 mg i.v., dexamethasone 10 mg i.v. (or equivalent), bronchodilators for bronchospasms, and other medications/treatment as medically indicated. Patients who have a grade 3 infusion reaction will not receive further IMC-A12 or cetuximab treatment, but will continue to be followed on the protocol.

- Grade 4: anaphylaxis (a life-threatening event characterized by the rapid onset [often within minutes] of airway obstruction [bronchospasm, stridor, hoarseness], urticaria, and/or hypotension)

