## **12.3 Analysis population**

Analysis of the primary endpoint will be performed only in the evaluable population.

Toxicity endpoints will be analyzed in the safety population.

Populations:

- Evaluable population: will comprise all randomized patients who receive at least one dose of the study drug(s) in this trial, based on the arm to which they were randomized. Additionally, the last treatment dose should have been administered within 10 days of the surgical resection. The evaluable population will only include patients whose both baseline and post-treatment tumor tissue samples are successfully analyzed for phospho-Akt levels. The reasons for non-evaluability in each arm will be assessed, at the time of the final analysis.
- Safety population: will include all patients who received any dose of an investigational product. The patients will be analyzed for product safety as part of the treatment actually received, regardless of which treatment they were randomized to receive.

For the studies involving assessment of intermediary metabolism parameters, arms B and C may be combined and compared / contrasted to arm A.

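### Section 5.1.2 permits a slower cetuximab infusion after a grade 3 allergic reaction, but Section 9.1.1 requires both drugs to be stopped for good

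*Combined protocol and SAP*

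**What the plan says.** Section 5.1.2 (Cetuximab) sets the dose, the infusion duration and the maximum rate, and then adds: "Infusion times may be increased for patients who experience grade 1 through 3 allergic reactions". The caution at the end of the same section points elsewhere for management: "In the event of an infusion reaction, the patient should be treated as described in Section 9.1.1".

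Section 9.1.1 (Cetuximab infusion reactions) fixes the grading scale: "Infusion reactions will be defined according to the NCI-CTCAE, Version 3.0, definition of allergic reaction/hypersensitivity, as follows". It then gives a rule for each grade. For the lower grades: "In the event of a grade 1 or 2 infusion reaction, the cetuximab infusion rate should be permanently reduced by 50" percent. For the higher grades the infusion is stopped immediately and the tubing disconnected, and afterwards: "Following a grade 3 or 4 infusion reaction, the patient is to receive no further cetuximab or IMC-A12 treatment".

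Section 9.2.1 (IMC-A12 infusion reactions) has the same rule for the other antibody: "Patients who have a grade 3 infusion reaction will not receive further IMC-A12 or cetuximab treatment".

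**The concern.** A grade 3 reaction, as 9.1.1 describes it, means bronchospasm needing parenteral medication, allergy-related edema or angioedema, or hypotension. The protocol's safety rule forbids re-exposure after such an event. The dosing section contains a sentence that allows it at a slower rate.

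The sentence sits in the section that staff consult when they prepare and run an infusion, so it is an operative instruction. These patients are awaiting planned resection and receive the drugs in a short preoperative biomarker study.

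Two other parts of the protocol make the conflict less harmless than it looks:

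- Section 10.1 allows dosing to resume after a hold for grade 3 toxicity that the investigator judges not clinically significant. It requires discontinuation of clinically significant grade 3 toxicity only when supportive care does not control it. Its listed exceptions do not include infusion reactions. Someone reading 5.1.2 and 10.1 together could find apparent support for re-treatment.
- Section 12.6.2 leaves hypersensitivity reactions out of the dose-limiting toxicity definition. A repeat grade 3 or 4 reaction would not count toward the Bayesian stopping boundaries, although serious adverse event reporting would still apply.

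**Working it through.** **Do the two sections grade the same events?** Section 5.1.2 speaks of allergic reactions and 9.1.1 of infusion reactions. Section 9.1.1 defines the latter by the CTCAE v3.0 allergic reaction/hypersensitivity term, so a given grade means the same thing in both places.

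**Comparison by grade**

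| Grade | Section 5.1.2 | Section 9.1.1 | Result |
|---|---|---|---|
| 1 | Longer infusion allowed | Rate cut by 50% | Compatible |
| 2 | Longer infusion allowed | Stop, treat, restart at 50% of the rate | Compatible |
| 3 | Longer infusion allowed | Stop, disconnect, neither drug given again | Direct conflict |
| 4 | Not mentioned | Stop, disconnect, neither drug given again | No conflict |

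No reading reconciles the two at grade 3. The current infusion has been disconnected and no later one may be given, so no infusion remains to be lengthened.

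**Which text is wrong?** Section 5.1.2 defers to 9.1.1 for infusion reactions, and 9.2.1 separately sets the same grade 3 stop for both drugs. Section 10.1 calls its rules general guidelines, so it does not displace the specific rule. The outlier is the sentence in 5.1.2.

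**How often could the conflict arise?** The plan has no figure of its own to reproduce. Cetuximab is given in arms A and C, planned at 20 each (Section 4.1): 20 + 20 = 40 patients. The per-patient grade 3 rate p is an assumption, taken from 1% to 5%, with patients treated as independent.

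- Expected number, 40 × p: 40 × 0.01 = 0.4; 40 × 0.05 = 2.
- Chance of at least one, 1 − (1 − p)^40: 1 − 0.99^40 = 0.331; 1 − 0.95^40 = 0.871.

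For a given p and 40 patients, the expected number wrongly re-treated after a grade 3 reaction cannot exceed the expected number of such reactions. It should be lower, because of the cross-reference to 9.1.1.

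**Does stopping correctly cost an evaluable patient?** Section 12.3 requires at least one dose, both tissue samples successfully analyzed for phospho-Akt, and this: "Additionally, the last treatment dose should have been administered within 10 days of the surgical resection". Section 4.1 puts dose 1 on day −9, give or take 3 days, with surgery on day 0. The interval is therefore 9 − 3 = 6 to 9 + 3 = 12 days. Counting the interrupted first infusion as a dose, a patient stopped after it meets the timing rule at 6, 7, 8, 9 or 10 days and misses it at 11 or 12. Section 4.1 also allows surgery to be moved up or postponed, which would shorten or lengthen the interval.

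**The case against.** The strongest reply is that the protocol already protects the patient. The caution in 5.1.2 sends staff to 9.1.1, which is specific and mandatory, whereas the faulty sentence is only permissive and sets out no restart procedure. A nurse must be in the treatment area and a physician close by, and doubts about grading go to the medical monitor. This stands as a reason to expect few errors in practice. It does not make the sentence right. The cross-reference says how a reaction is to be treated, which could be read as acute care only, leaving the next infusion's duration to the dosing section.

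A second reply is that the 1% to 5% rate has no source in the documents, that the contradiction needs no rate, and that an assumed expectation cannot cap an observed count. All of that is fair. The arithmetic only indicates scale, and its bound applies to expected counts at the assumed rate. Section 12.4 also allows extra enrollment to reach 18 evaluable patients per arm, so 40 is the plan and not a ceiling.

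Third, the evaluability point follows from applying 9.1.1 correctly and is the same before and after the correction. That is true. Its use is limited to showing that a patient properly stopped after dose 1 is not automatically lost to the primary analysis.

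Finally, a corrected sentence that keeps the word may is softer than the 50% reduction in 9.1.1. However, 9.1.1 itself keeps the rate unchanged for a grade 1 or 2 reaction that is only delayed drug fever, so permissive wording with a reference to 9.1.1 is compatible with that section.

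**Conclusion.** The concern holds. Sections 5.1.2 and 9.1.1 conflict at grade 3 on a patient-safety rule, 9.1.1 governs, and the permission in 5.1.2 is a wording error that should be corrected. The conclusion rests on the text alone.

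The indication of scale (0.4 to 2 expected grade 3 reactions, 33% to 87% chance of at least one) depends on the assumed rate and on 40 cetuximab-treated patients. It describes how often the conflict would come into play, not how often harm would follow. Power, type I error, sample size and the primary analysis are unaffected.

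**What to change.** In the 5.1.2 sentence, change the grade range from 1 through 3 to 1 or 2, and add a reference to Section 9.1.1. Add a clause stating that after a grade 3 or 4 reaction neither cetuximab nor IMC-A12 is given again. Leave 9.1.1 and 9.2.1 as they are.

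Deleting the sentence and relying on the existing cross-reference would also remove the conflict. Stating the grade 3 stop in the dosing section is safer, because that is where infusion staff will look.

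The cost is a one-sentence amendment, with no change to design, sample size or analysis.
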